11.3.13 Pregnancy Test

Positive pregnancy test results of females of childbearing potential will be presented in a data listing.

11.4 SUBGROUP ANALYSES FOR SAFETY VARIABLES

Subgroup analyses for safety variables are not planned, but may be performed.

12.0 **HEALTH OUTCOMES ANALYSES**

Not applicable.

13.0 INTERIM ANALYSIS

No interim analysis is planned for this study. Each database lock will correspond to a milestone and statistical analysis will be provided when all randomized patients have either completed or exited from the targeted visit (Weeks 12, Week 52, and Month 20/Exit).

14.0 **DETERMINATION OF SAMPLE SIZE**

The sample size calculation is based on the primary efficacy analysis of the time-matched IOP for US FDA review because the sample size based on the primary efficacy analysis for other regions is expected to be smaller.

The sample size is estimated based on a 2-sided t-test with $\alpha = 0.05$ at each timepoint and the assumption that the mean IOP difference between Bimatoprost SR 10 μg and timolol is -0.25 mm Hg (ie, Bimatoprost SR 10 μg is 0.25 mm Hg better in IOP-lowering than timolol) at Weeks 2 and 6 and 0 mm Hg at Week 12, with a common SD of 4.0 mm Hg and a common within-subject correlation of 0.6. It is also assumed that the efficacy (IOP-lowering effect) of Bimatoprost SR 15 μg is better than that of Bimatoprost SR 10 μg by 0.25 mm Hg at each timepoint (Hours 0 and 2). These assumptions are based on the data obtained from the ongoing clinical study 192024-041D. Based on simulations, a sample size of 540 patients (180 per group) will provide approximately 95% and 81% power to show noninferiority of Bimatoprost SR 15 μg and Bimatoprost SR 10 μg , respectively, to timolol at all 6 scheduled timepoints based on a noninferiority margin of 1.5 mm Hg and at 3 or more timepoints based on a noninferiority margin of 1.0 mm Hg. Assuming a premature discontinuation rate of 10% within 12 weeks (before primary database lock), approximately 600 patients (200 per group) are to be enrolled into this study.

[figure not shown]
15.0 **STATISTICAL SOFTWARE**

[figure not shown]
Statistical analyses will be performed [REDACTED]

16.0 **DATA HANDLING CONVENTIONS**

16.1 **VISIT TIME WINDOWS**

For all analyses, all follow-up visits or the exit visit will be reassigned with the visit number based on the study days

[REDACTED]

[REDACTED]

[REDACTED]

16.2 DERIVED VARIABLES

No Applicable.

16.3 REPEATED OR UNSCHEDULED ASSESSMENTS OF SAFETY PARAMETERS

If a patient has repeated assessments before the start of the first treatment, unless otherwise stated, the results from the final nonmissing assessment made prior to the start of the study treatment will be used as baseline. If end-of-study assessments are repeated or if unscheduled visits occur, the last nonmissing postbaseline assessment will be used as the end-of-study assessment for generating summary statistics. However, all postbaseline assessments will be used for safety evaluation, and all assessments will be presented in the data listings.

16.4 MISSING SEVERITY ASSESSMENT FOR ADVERSE EVENTS

If severity is missing for an AE that started before the date of the first dose of study treatment, an intensity of mild will be assigned. If severity is missing for an AE that started on or after the date of the first dose of study treatment, an intensity of severe will be assigned. The imputed values for severity assessment will be used for the incidence summary; the values will be shown as missing in the data listings.

16.5 MISSING CAUSAL RELATIONSHIP TO STUDY TREATMENT FOR ADVERSE EVENTS

If the causal relationship to the study treatment is missing for an AE that started on or after the date of the first dose of study treatment, a causality of yes will be assigned. The imputed values for causal relationship to study treatment will be used for the incidence summary; the values will be shown as missing in the data listings.

16.6 MISSING DATE INFORMATION FOR ADVERSE EVENTS

The following imputation rules only apply to cases in which the start date for AEs is incomplete (ie, partly missing).

Missing Month and Day

- If the year of the incomplete start date is the same as the year of the first dose of study treatment, the month and day of the first dose of study treatment will be assigned to the missing fields.
- If the year of the incomplete start date is before the year of the first dose of study treatment, *December 31* will be assigned to the missing fields.
- If the year of the incomplete start date is after the year of the first dose of study treatment, *January 1* will be assigned to the missing fields.

Missing Month Only

- If only the month is missing, the day will be treated as missing and both the month and the day will be replaced according to the above procedure.

Missing Day Only

- If the month and year of the incomplete start date are the same as the month and year of the first dose of study treatment, the day of the first dose of study treatment will be assigned to the missing day.
- If either the year of the incomplete start date is before the year of the date of the first dose of study treatment or if both years are the same but the month of the incomplete start date is before the month of the date of the first dose of study treatment, the last day of the month will be assigned to the missing day.
- If either the year of the incomplete start date is after the year of the date of the first dose of study treatment or if both years are the same but the month of the incomplete start date is after the month of the date of the first dose of study treatment, the first day of the month will be assigned to the missing day.

If the stop date is complete and the imputed start date as above is after the stop date, the start date will be imputed by the stop date.

If the start date is completely missing and the stop date is complete, the following algorithm will be used to impute the start date:

- If the stop date is after the date of the first dose of study treatment, the date of the first dose of study treatment will be assigned to the missing start date.
- If the stop date is before the date of the first dose of study treatment, the stop date will be assigned to the missing start date.

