1.3.3 Clinical Study with Bimatoprost SR

Study 192024-041D was a Phase 1/2, paired-eye comparison evaluating the safety and efficacy of 4 dose strengths of Bimatoprost SR (6 µg, 10 µg, 15 µg, or 20 µg [2 × 10 µg implants]), as single or repeat administration in one eye (study eye), versus the use of topical LUMIGAN[®] 0.03% in the fellow eye (nonstudy eye). The objective of this study was to evaluate the safety and IOP-lowering efficacy of Bimatoprost SR in patients with OAG.

A total of 109 patients received a single administration and 24 patients received a repeat administration of Bimatoprost SR. A trend in dose-response was observed across the 4 dose strengths that were tested. Data suggest that the implant may provide topical prostaglandin analog-like efficacy up to 3 to 4 months post-implantation in the majority of patients. Data following the second administration in the redosed patients showed similar IOP lowering to that observed following the first administration of Bimatoprost SR.

Bimatoprost SR showed an acceptable safety profile with single and repeat administrations in Study 192024-041D. Most adverse events were ocular, mild or moderate in severity, occurred within the first 2 days after Bimatoprost SR administration, and were considered related to the study drug administration procedure. There were no reports of serious study drug-related adverse events, and no new safety concerns were observed after the second treatment. Please refer to the Investigator's Brochure for details on reported safety findings.

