The number and percentage of patients reporting nonocular TEAEs in each treatment group will be tabulated by SOC and preferred term. Also the number and percentage of patients reporting treatment-related (including study drug related or injection procedure related) nonocular TEAEs in each treatment group will be tabulated by SOC and preferred term.

Similar analyses will be done for ocular TEAEs including 1) by PT and severity; 2) treatment-related TEAEs by PT for each treatment group by study eye and fellow eye. In addition, similar analyses will be performed for ocular TEAEs by treatment cycle.

Within each treatment cycle, ocular TEAEs identified (onset or worsened) within 2 days of administration and identified more than 2 days of administration of each cycle will be summarized by each treatment group for study eye and pooled for fellow eye.

Serious TEAEs

Nonocular and ocular STEAEs will be summarized by preferred term and treatment group, respectively.

TEAEs Leading to Study Discontinuation

Nonocular TEAEs and ocular TEAEs leading to premature discontinuation of the study will be summarized by preferred term and treatment, respectively.

Similarly, ocular TEAEs leading to premature discontinuation will also be tabulated by treatment group by treatment cycle.

Ocular TEAEs Leading to Study Drug Discontinuation or Regimen Change

Ocular TEAEs leading to study drug discontinuation will be summarized by preferred term and treatment for the entire study period and also for each cycle. Ocular TEAEs leading to study drug discontinuation or regimen change are defined as the ocular TEAEs with action regarding study drug reported as “Discontinued” or “Regimen Changed” on the eCRF AE form.

Ocular TEAEs Leading to Implant Removal

Ocular TEAEs leading to implant removal will be summarized by preferred term and treatment for the entire study period and also for each cycle.

[REDACTED]

[REDACTED]

[REDACTED]

[REDACTED]

[REDACTED]

[REDACTED]

[REDACTED]

[REDACTED]

[REDACTED]

[REDACTED]

[REDACTED]

[REDACTED]

[REDACTED]

[REDACTED]

[REDACTED]

[REDACTED]

[REDACTED]

[REDACTED]

[REDACTED]

[REDACTED]

[REDACTED]

[REDACTED]

[REDACTED]

[REDACTED]

[REDACTED]

[REDACTED]

[REDACTED]

[REDACTED]

[REDACTED]

[REDACTED]

[REDACTED]

[REDACTED]

[REDACTED]

[REDACTED]

[REDACTED]

[REDACTED]

[REDACTED]

[REDACTED]

[REDACTED]

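### SAP 16.6 dates incompletely dated adverse events to the first dose, which inflates the early group of the Cycle 1 two-day split in SAP 11.1; the net effect on the late group depends on which date parts are missing

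*SAP*

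**What the plan says.** SAP 16.6 opens by limiting itself to incomplete dates: "The following imputation rules only apply to cases in which the start date for AEs is incomplete (ie, partly missing". Three of its branches use the first-dose date.

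- **Day missing, first-dose month and year:** "the day of the first dose of study treatment will be assigned to the missing day".
- **Month and day missing, first-dose year:** "the month and day of the first dose of study treatment will be assigned to the missing fields".
- **Start fully missing, complete stop date after first dose:** "the date of the first dose of study treatment will be assigned to the missing start date".

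For a missing day in a month after the first-dose month, "the first day of the month will be assigned to the missing day". No branch refers to the 2nd or 3rd administration. A cap applies "If the stop date is complete and the imputed start date as above is after the stop date"; it moves a start back to the stop date and cannot correct a start that is already too early.

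SAP 11.1 assigns treatment-emergent events to cycles by onset date. Within each cycle it summarizes ocular events identified "within 2 days of administration and identified more than 2 days of administration of each cycle".

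SAP 16.4 (severity) and 16.5 (causality) state that imputed values serve the incidence summary and appear as missing in listings. SAP 16.6 sets no such limit on use.

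**The concern.** Placing an uncertain onset on the first-dose date is cautious for one question: whether the event is treatment-emergent. The two-day split asks a different question, namely how long after administration the event began. There the same date acts as an observed onset time of zero days, and the event counts as early whatever its true onset.

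This matters because Protocol 1.3.3 reports that most adverse events in the earlier Phase 1/2 study "occurred within the first 2 days after Bimatoprost SR administration, and were considered related to the study drug administration procedure". The new table will naturally be read against that pattern. A rule that turns unknown timing into early timing could give the pattern some apparent support that comes from missing dates.

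**Working it through.** The plan gives no figure to reproduce, so the check applies the SAP 16.6 rules to known onsets and compares the true category with the imputed one.

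**Inputs.** Administrations on days 0, 112 and 224 (16-week intervals, Protocol 5.10); date rules from SAP 16.6; cycle assignment and split from SAP 11.1.

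**Assumptions.** Every first-dose date in one 365-day year; every true onset day from 0 to 363, equally weighted; every date incomplete; no stop date available. Early means at most 2 days after administration, with at most 1 day as a check. Counts are combinations of dose date and onset day, not expected events.

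**Step 1: first-dose branches.**

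| Missing part | True late onsets in scope | Counted as Cycle 1 early |
|---|---|---|
| Day, in first-dose month (≤ 2 days) | 4,679 | 4,679 |
| Same (≤ 1 day) | 5,020 | 5,020 |
| Month and day, in first-dose year (≤ 2 days) | 64,526 | 64,526 |
| Same (≤ 1 day) | 65,279 | 65,279 |

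The last two rows include late events from Cycles 2 and 3. Example: dose on 3 June, true onset 28 June (25 days later), day missing; the onset becomes 3 June and the event is early.

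**Step 2: first-of-month branch.** Example: same patient, 2nd administration 23 September (3 June + 112 days), true onset 24 September, day missing. The onset becomes 1 September and the event is Cycle 1 late. With only the day missing, 93.4% of true early onsets after the 2nd or 3rd administration move this way (95.1% with ≤ 1 day).

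**Step 3: net effect, ≤ 2 days.**

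| Category | True | Day missing | Month and day missing |
|---|---|---|---|
| Cycle 1 early | 1,095 | 6,468 | 67,519 |
| Cycle 1 late | 39,785 | 39,804 | 33,463 |
| Cycle 2 late | 39,785 | 39,771 | 21,255 |
| Cycle 3 late | 50,005 | 44,621 | 9,453 |

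With only the day missing, Cycle 1 late loses 6,468 − 1,095 = 5,373 combinations to Cycle 1 early. It gains 5,392 from Cycle 2 (1,023 early and 4,369 late onsets in the calendar month of the 2nd administration). So 39,785 − 5,373 + 5,392 = 39,804, almost no change. Cycle 1 early rises by a factor of 6,468 / 1,095 = 5.9. With month and day missing, the late total falls in every cycle.

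**Step 4: share misplaced in the first-dose month.** Take a 30-day month with onset uniform over the remaining days.

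- Weighting dose days by days remaining, the share truly in the first 2 or 3 calendar days is 59/465 = 12.7% or 87/465 = 18.7%, so 81–87% are misplaced.
- Weighting each patient equally, it is 23.3% or 31.6%, so 68–77% are misplaced.
- If true onsets cluster early, fewer are misplaced.

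**Step 5: event count, on assumed inputs.** Neither input is in the documents. With 20–40 late ocular events per arm in the first-dose month and 2–10% incompletely dated, 20 × 0.02 = 0.4 to 40 × 0.10 = 4 events per arm of about 200 would move.

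**The case against.** The strongest reply is that this will hardly matter. Only incompletely dated events are touched, and the first month has close contact: a Day 2 visit, Day 4 and Day 8 calls and a 2-week visit (Protocol 5.10), with adverse events queried at each visit (Protocol 9.1.1). A missing day is least likely there. That stands. The count may be nil, and Step 5 is only illustrative.

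Handling of imputed dates in this table may also be set out elsewhere. SAP 4.0 puts table specifications in a separate document, and SAP text after the split is redacted. That stands too, so the point concerns what the readable SAP text leaves unsaid.

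A reader might infer three stronger claims that the documents do not support.

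- **That the late group is understated in general.** Step 3 shows that the net direction depends on the mix of missing date parts.
- **That the split is how the plan separates procedure effects from drug effects.** SAP 11.1 does that through attribution on the eCRF, determined by the investigator under Protocol 9.1.4; date imputation does not alter that attribution. Protocol 1.3.3 only summarizes an earlier study.
- **That about four in five affected events are misplaced.** That figure needs uniform onset and weighting by days remaining. If the earlier study's pattern held for these events, fewer than half would be misplaced.

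**Conclusion.** The point holds in limited form. Under the first-dose branches of SAP 16.6, an incompletely dated ocular event always enters the early group of Cycle 1 (unless a stop date before first dose makes it pre-dose), and the Cycle 1 early group is inflated whenever such events truly began later. The first-of-month branch causes errors in the other direction around the 2nd and 3rd administrations. The net effect on the late groups is therefore not determined: close to zero for Cycle 1 when only the day is missing and onset is uniform, and downward when the month is missing too.

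The number of events is unknown. The only table at issue is descriptive, and no hypothesis test or efficacy conclusion depends on it. The rule remains cautious for treatment-emergent status. This is a low-priority improvement.

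**What to change.** State in SAP 16.6 that imputed start dates decide treatment-emergent status only. State in SAP 11.1 that, in the two-day split for every cycle, an event is early or late only when recorded information establishes it. Such information includes a known month that settles the matter, a complete stop date, or the Day 2 visit record. A Day 4 or Day 8 call shows that an event existed by then; alone it does not prove onset within 2 days. Show the remaining events in a timing-not-known row, with a sensitivity line counting them as late.

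This deals with both directions of error. Re-anchoring imputed dates to the latest administration would not: it would extend the early shift to Cycles 2 and 3.

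Cost: one or two SAP sentences, one small extra row and the sensitivity line.

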5.10 Retreatment

Administration of Bimatoprost SR will occur at fixed intervals of 16 weeks, up to a total of 3 administrations. Patients will be readministered the Bimatoprost SR dose strength to which they were randomized unless in the investigator's opinion it would not be in the best interest of the patient to readminister Bimatoprost SR based on previous adverse events or safety concerns. Patients who have been treated with nonstudy IOP-lowering medication in only one eye will still attend administration visits; if the treated eye is the Bimatoprost SR study eye, the patient will receive a Sham administration in that eye. Control group study eyes and fellow eyes that have been treated with nonstudy IOP-lowering medications will continue to receive Sham administrations. Patients who have been treated with nonstudy IOP-lowering medication in both eyes will not attend the Administration Day visits, nor will they attend the Day 2, Days 4 and 8 (phone call), or the 2-week visits (ie, Weeks 2, 18, and 34) following an administration.

6. Response Measures and Summary of Data Collection Methods

Detailed information on equipment and methodology to be used is provided in the Protocol Procedure Manual.

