11.0 SAFETY ANALYSES

The safety analysis will be performed using the safety population. The safety parameters will include the following nonocular safety parameters: nonocular AEs, clinical laboratory values, vital signs, and pregnancy; [REDACTED]

[REDACTED] Unless otherwise stated, the last nonmissing safety assessment before the first dose of study treatment will be used as the baseline for all analyses of that safety parameter. Continuous variables will be summarized by number of patients and mean, SD, median, the 1st quartile and the 3rd quartile, minimum, and maximum values. Categorical variables will be summarized by number and percentage of patients.

[REDACTED]

For all safety by-cycle summary analyses, in order to compare cycles of similar duration, the data included in each cycle will be,

- Cycle 1 (16 weeks): data from the 1st injection to the 2nd injection date -1 or upper bound of week 15 visit window (section 16.1) if a patient didn't receive the 2nd injection;
- Cycle 2 (16 weeks): data from the 2nd injection to the 3rd injection date -1 or upper bound of week 31 visit window (section 16.1) if a patient didn't receive the 3rd injection;
- Cycle 3 (20 weeks): data from the 3rd injection to upper bound of week 52 visit window (section 16.1);
- Extended safety follow up: data after week 52 for patients with 3 injections and extended follow up.

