11.1 ADVERSE EVENTS

Adverse events will be coded by SOC and preferred term using the Medical Dictionary for Regulatory Activities.

For a given AE and patient, if more than 1 severity grade is reported, the worst severity grade (the greater of the onset and maximum severity recorded on the electronic case report from [eCRF]), will be used for analysis.

Adverse events will be classified into ocular AEs and nonocular AEs. An ocular AE will be determined as indicated on the AE form of eCRF, and thus are not limited to AEs with primary SOC of eyes. The treatment-related ocular AEs will be further broken down by either related to injection procedure or related to study drug as indicated on eCRF. Ocular AEs will be tabulated by treatment group for the study eye and pooled for the fellow eye, and nonocular AEs will be summarized by treatment group for patient. Analysis by cycle of treatment will also be performed.

Treatment-Emergent Adverse Events

An AE will be considered a treatment-emergent adverse event (TEAE) for the study treatment period if the AE meets 1 of the following criteria:

- The onset date is on or after the first study treatment date.
- The onset date is before the first study treatment date and either:
 - The severity of the event worsened on or after the first treatment date.
 - The event became serious on or after the first study treatment date.

An AE will be considered as a TEAE for a treatment cycle if the AE meets 1 of the following criteria:

- The onset date is on or after the treatment administration of the cycle but prior to the next cycle administration.
- The onset date is before the treatment administration of the cycle and either:
 - The severity of the event worsened on or after the treatment administration of the cycle.
 - The event became serious on or after the treatment administration of the cycle.

Overall summary of TEAEs will be provided on a per-patient basis for categories of all TEAEs, treatment-related TEAEs, injection procedure-related TEAEs, study drug-related TEAEs, serious TEAEs (STEAEs), deaths, and TEAEs leading to study discontinuation. Each category (except deaths) will be further classified into ocular and nonocular subcategories.

The number and percentage of patients reporting TEAEs will be provided on a per-patient basis by 1) SOC and preferred term; 2) SOC, preferred term and severity in descending order of frequency for each treatment group.

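### Adverse events with a missing day in the month of the 2nd or 3rd administration are dated to the 1st, so most of those that followed the administration are tabulated in the previous cycle

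*SAP*

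**What the plan says.** SAP 16.6 gives three cases for a start date that lacks only the day. In the month of the first dose, the first-dose date is used. In an earlier month, the last day of that month is used. If the year is later, or if the years agree and "the month of the incomplete start date is after the month of the date of the first dose of study treatment", then "the first day of the month will be assigned to the missing day". One check follows, for events with a fully known end: when "the imputed start date as above is after the stop date, the start date will be imputed by the stop date". The legible text of 16.6 does not mention the Week 16 or Week 32 administration.

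Protocol 5.10 sets the schedule: "Administration of Bimatoprost SR will occur at fixed intervals of 16 weeks, up to a total of 3 administrations".

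SAP 11.0 bounds the cycles by the administration dates: "Cycle 1 (16 weeks): data from the 1st injection to the 2nd injection date -1" and "Cycle 2 (16 weeks): data from the 2nd injection to the 3rd injection date -1", with a visit-window limit for patients who miss the next injection. SAP 11.1 counts an event as treatment-emergent for a cycle when "The onset date is on or after the treatment administration of the cycle but prior to the next cycle administration". An event with earlier onset also counts if it worsened or became serious on or after that cycle's administration. SAP 11.1 further divides, within each cycle, "ocular TEAEs identified (onset or worsened) within 2 days of administration" from those identified later.

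**The concern.** In the first-dose month the SAP resolves an unknown day in the cautious direction: the event is taken to start with treatment. SAP 16.4 and 16.5 do the same for missing severity and missing causality after the first dose. In the months of the second and third administrations the direction reverses. The day becomes the 1st, which is before the administration unless that fell on the 1st. An event that followed the repeat procedure is then placed in the preceding cycle and counted as arising long after that cycle's administration.

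Safety after repeat administration is part of the study's stated hypotheses. The by-cycle tables and the 2-day split are the planned displays that bear on it most directly. Protocol 1.3.3 reports that in the Phase 1/2 study most adverse events occurred in the first 2 days after administration, so events soon after a repeat procedure are the ones these tables need to place correctly.

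**Working it through.** The plan gives no figure to reproduce. The inputs are the SAP 16.6 missing-day rule, the SAP 11.0 and 11.1 cycle boundaries, and the 16-week interval (112 days) from Protocol 5.10.

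**1. Which rule applies.** Because 112 days is longer than any month, the second and third administrations are never in the first-dose month. Enumerating all 1,461 first-dose dates in a 4-year span, with later administrations at +112 and +224 days, gave 0 exceptions. An assumed shift of ±7 days in the second administration changed nothing. The stop-date check can only move a start date earlier, so it cannot restore these events to the later cycle.

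**2. Example.** First dose 25 Jan 2016; second administration 112 days later, 16 May 2016; true onset 17 May with the day missing. The imputed onset is 1 May, which is in Cycle 1 and 112 − 15 = 97 days after the first administration.

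**3. Events that truly followed the administration in the same month.** They are placed correctly only if the administration was on the 1st. With administration day and onset day counted as equally likely pairs in a 30-day month:
- onset 0–2 days after: 30 + 29 + 28 = 87 pairs, of which 3 have the administration on the 1st; wrong in 84/87 = 96.6%
- onset any later day of the month: 465 pairs, 30 with the administration on the 1st; wrong in 435/465 = 93.5%

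The calendar enumeration gives 96.6% (0–2 days), 96.4% (0–6 days) and 93.6% (0–30 days).

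**4. All missing-day events in that month, including those before the administration.** Let p be the share on days 0–2, with the rest uniform over the month and the administration day uniform on 1–30, ignoring the small edge effect at month end.
- SAP rule, clustered events: wrong in 29/30 = 96.7%
- SAP rule, uniform events: onset on or after an administration that was not on the 1st, 435/900 = 48.3%
- Extended rule (administration date assigned): clustered events 0% wrong; uniform events wrong if onset truly preceded the administration, 435/900 = 48.3%

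Wrong-cycle share: SAP = p × 96.7% + (1 − p) × 48.3%; extended = (1 − p) × 48.3%.

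| p | SAP rule | Extended rule |
|---|---|---|
| 0% | 48% | 48% |
| 50% | 72.5%, about 73% | 24% |
| 80% | 87% | 10% |

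**5. The 2-day split under the same model.** The extended rule puts every such event on day 0.
- Uniform events truly within 2 days: 87/900 = 9.7%. The extended rule is wrong for the other 813/900 = 90.3%.
- SAP rule, uniform events: wrong for 87 − 3 = 84 pairs within 2 days, plus 27 pairs with the administration on the 1st and later onset; 111/900 = 12.3%.
- Clustered events: SAP wrong in 96.7%, extended 0%.

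| p | SAP rule | Extended rule |
|---|---|---|
| 0% | 12% | 90% |
| 50% | 0.5 × 96.7 + 0.5 × 12.3 = 54.5% | 0.5 × 90.3 = 45% |
| 80% | 0.8 × 96.7 + 0.2 × 12.3 = 80% | 0.2 × 90.3 = 18% |

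The two are equal when p × 96.7 = (1 − p) × (90.3 − 12.3), that is p = 78.0/174.7 = 45%.

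**The case against.** Anchoring imputation to the first dose is a coherent way to settle treatment-emergent status, and several things limit the consequence.

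- **Clustering is assumed.** Protocol 1.3.3 describes the timing of adverse events in general, not of those with an unknown day. A missing day is arguably least likely soon after a procedure: patients are observed for at least 1 hour and told to report events at once (Protocol 5.9.4), and a Day 2 visit, Day 4 and Day 8 calls and a 2-week visit follow (Protocol 5.6.1). This stands. It is why the 0% row must be shown, where the two rules are equally wrong on cycle.
- **Other safety tables are untouched.** Whole-study TEAE totals do not move. Relation to the injection procedure comes from the eCRF, not from imputed dates. An event recorded as worsening or becoming serious after an administration still counts in the new cycle. All of this stands.
- **The rule is the same in every arm.** True, but the comparison affected is between cycles, and identical treatment of the arms does not correct that.
- **Dating every such event to day 0 can damage the 2-day split.** This stands, as step 5 shows, and it shapes the fix.

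A reader might infer that nearly all events after a repeat administration are misplaced. The documents do not support that: complete dates are unaffected, and a missing day in a later month is still dated after the administration. If onset is spread evenly over the 112 days after administration, about 13% of all missing-day post-administration events are misassigned. A reader might also infer that Cycles 2 and 3 are both understated. Cycle 2 loses events to Cycle 1 but gains them from Cycle 3, so its net direction cannot be stated.

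**Conclusion.** The gap is real but narrow. For events with a missing day in the month of the second or third administration and true onset after it, about 94–97% go to the previous cycle. That result needs only the calendar and the SAP's own rules. The direction is settled for two cycles: Cycle 1 only gains such events and Cycle 3 only loses them.

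The 48%, 73% and 87% shares among all missing-day events in that month depend on an assumed clustering of 0%, 50% and 80%, for which the documents give no figure. Extending the first-dose rule is never worse for cycle assignment in this model and is better with any clustering.

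The absolute effect is unknown, because the documents give no count of partly dated events. It is probably small, given the close contact after each procedure. Nothing in the documents shows that an efficacy result or a whole-study safety conclusion depends on this. It is a minor correction to the by-cycle tables and the 2-day split. Redacted parts of the safety sections could not be checked.

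**What to change.** In SAP 16.6, for by-cycle assignment, add: if the known month and year match those of any administration the patient received (1st, 2nd or 3rd, Sham included), assign that administration date; otherwise keep the existing rules, including the 1st of the month for later months. Apply this before the stop-date check, so that a complete stop date before the administration still returns the event to the earlier cycle. At 16-week spacing no month contains two administrations, so the rule is unambiguous.

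In SAP 11.1, do not treat an imputed day as observed in the 2-day split. Either show these events in a separate line for unknown onset day, or count them as within 2 days and state that this is a conservative convention.

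The cost is a sentence in each section and a small derivation change. The downside is that some events truly before the re-administration will be counted in the later cycle, the same cautious direction already used for the first dose. If they are counted as day 0, the within-2-days table may be inflated. Reporting the number of events with an imputed day, by cycle, would let readers judge both effects.
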